Overall Strategy. This is a prospective, randomized, repeated measures single- blind clinical trial. The purposes of this study are to 1) stratify patient risk for second ACL injury, and 2) determine the effects of differential treatment intervention, including targeted neuromuscular training (TNMT), home program only (HOME) and standard clinical (STAN) training, on clinical, biomechanical, and neuromuscular performance measures associated with an increased secondary ACL injury risk. At this time there is no evidence to support one intervention as either superior or inferior to the other interventions proposed in this study. After the initial ACL injury and study enrollment, all patients will participate in standardized pre-operative rehabilitation. They will then undergo surgery by a fellowship-trained sports medicine surgeon at Mayo Clinic, Rochester, MN. Data for Aim 1 will be obtained from biomechanical, neuromuscular and clinical testing performed during Pre-Testing. Data for Aim 2 and the Exploratory Aim will be obtained from biomechanical and clinical test results obtained from Pre- and Post-Testing time points.

Common Rehabilitation. All study participants will follow the same rehabilitation guidelines before and immediately after surgery, until they are cleared by their attending surgeon to return to full participation in sports. After clearance, they will be randomized into the differential treatment groups. Entry into this phase is criteria-based, and represents the standards identified in the literature for entry into the final phase of rehabilitation. These criteria include: symmetrical knee range of motion; minimal or no pain and knee effusion; quadriceps strength $\geq 80\%$ compared to contralateral limb (180°/sec and 300°/sec); self-report of function $\geq 80\%$; limb symmetry index during single leg hop for distance $\geq 80\%$. Both pre- and postoperative rehabilitation protocols are a composite of previously published, evidence-based protocols from expert researchers and clinicians.⁶⁵⁻⁶⁷

Differential Rehabilitation. Once study participants are cleared for full participation in sports, they will be randomized into one of three groups for differential treatment. This will include HOME, STAN and TNMT

groups. If patient lives at a distance from Mayo Clinic and cannot participate in the weekly training but is able to come to both testing session they will be randomized into the HOME and STAN programs.

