HOME Program is distinguished by patients participating in a home only intervention that consists of running exercises performed twice a week for six to eight weeks. No plyometric or agility drills are performed in this study arm. This represents the minimal intervention to prepare for a return to sports. No neuromuscular training or movement training beyond the sagittal plane will be performed.

Patients in the STAN group will be used as the control group. They will receive no training. They will participate in the two testing sessions and the weekly survey updates.

Patients who are enrolled in the TNMT group will participate in 12 sessions of supervised outpatient physical therapy over a six to eight week period. The TNMT protocol is distinguished by performance of exercises designed to enhance core and hip strength, performance of neuromuscular training exercise that are designed to correct movement flaws associated with second ACL injury²⁵, providing verbal and visual feedback and performance of single leg drills on both legs.

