6. One (1) static digitizing probe for creating calibration marker locations on hard-to-reach anatomical landmarks.
7. Two (2) Visual 3D motion analysis software licenses (C-motion inc., Germantown, MD)
8. Two (2) Microsoft Kinect 3D cameras (Microsoft Corp., Redmond, WA)
9. Two (2) Wii Balance boards (Nintendo of America, Inc., Redmond, WA)
10. Two HumacNORM isokinetic and isometric dynamometers with accompanying software (Figure FE2, CSMi, Stoughton, MA).
11. Two Humac balance devices with accompanying software (CSMi, Stoughton, MA).
12. One GNRB arthrometer (Genourob, Laval, France)
13. Two (2) complete Simi Aktisys marker-based and marker-less motion analysis systems with associated cameras, hardware, and software (Simi Reality Motion Systems GmbH, Unterschleissheim, Germany).
14. Thirteen (13) Dartfish Motion Pro Premium licenses with fourteen (14) associated cameras and necessary hardware split between Mayo Clinic Rochester and Mayo Clinic Square facilities (Dartfish USA, Inc., Alpharetta, GA).

Computer/Office

Adequate dedicated office space and computing capabilities already exists within the laboratories and clinical facilities to meet the needs of all personnel included in this project. Each listed clinical and laboratory space also has designated multimedia conference room space with teleconferencing capabilities. All key personnel have office space in both Minneapolis and Rochester SMCs.

(1a) This is a multisite study involving Mayo Clinic and non Mayo Clinic sites. *When checked, describe in detail the research procedures or activities that will be conducted by Mayo Clinic study staff.*

(1b) Mayo Clinic study staff will be engaged in research activity at a non Mayo Clinic site. *When checked, provide a detailed description of the activity that will be conducted by Mayo Clinic study staff.*

Subject Information

Target accrual: This study will enroll 150 subjects. Anticipating a 30% dropout rate, this will yield a final accrual of 120 subjects.

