Check 'None' when none of the identifiers listed above will be recorded, maintained, or shared during the conduct of this study. (exempt category 4)	 None	 None

Data Analysis

Power analyses and study endpoints are not required for minimal risk research, pilot or feasibility studies.

No statistical information. *If checked, please explain:*

Power Statement:

We expect that the minimal clinically significant effect size of TNMT on knee biomechanics is 0.17 or above. Using an a priori power analysis based on repeated measures ANOVA, we expect that to achieve 80% power with $\alpha = 0.05$, this study will require a final accrual of 87 subjects. This assumes a correlation coefficient of 0.3 among the repeated measures, which is likely conservative. Thus, an accrual of 116 (with an estimated 30% dropout rate) subjects will be sufficient to determine if a clinically significant reduction in unininvolved limb transverse plane hip net moment impulse, frontal plane knee joint ROM, initial contact sagittal plane knee moment asymmetry, and deficits of involved limb postural stability has occurred as a result of TNMT. This sample size provides adequate power for all variables of interest for Aims 1 and 2. Mayo Clinic averages more than 120 ACLR per year in the Minneapolis/Rochester region on individuals under age 25. Thus, the available patient pool is more than adequate to meet study requirements.

Data Analysis Plan:

Aim 1: We will utilize normal mixture based clustering analysis⁷⁰ to identify groups with distinguished risks based on a priori covariates (i.e., demographics and biomechanical variables). Our previous work used a similar approach to effectively cluster subjects into three distinct risk groups. We intend to confirm disparate risk for injury by assessment of the magnitude of differences across groups using knee and hip abduction angles, surrogates for ACL injury.

The normal mixture model approach works by assuming the density of the covariates for a subject x , can be described as:

$$f(x) = \sum_{k=1}^K \pi_k \phi(x; \mu_k, \Sigma_k),$$

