where (i) K is the number of mixture components (groups), (ii) π_k is the unconditional probability that a subject fall into the k th group, and (iii) $\phi(\cdot; \mu, \Sigma)$ is the multivariate normal density with mean μ and covariance Σ . Estimates of the parameters, π_k, μ_k, Σ_k , are typically obtained using maximum likelihood. The number of groups is most commonly chosen to optimize the Bayesian Information Criterion (BIC). Often assumptions such as a common covariance matrix for all k , or common shape (i.e., correlation) matrix, are made to make estimation feasible, depending on the size of data, and these decisions are also commonly made on the basis of BIC. In this work we intend to assume a common Σ , and assess the validity of this assumption via model diagnostics. Once parameter estimates are obtained, clustering is performed by calculating the probability of group membership m for a given subject, conditional on his/her covariate values, i.e.,

$$P(m = k | x) = \frac{\pi_k \phi(x; \mu_k, \Sigma_k)}{\sum_{l=1}^K \pi_l \phi(x; \mu_l, \Sigma_l)}.$$

The subject will then be assigned to the group k that results in the largest conditional group membership probability $P(m = k | x)$. This approach has been shown to perform very well in the presence of a large number of variables with the inclusion of a variable selection mechanism.^{71, 72} We will leverage such an approach in our analysis to identify a reduced set of biomechanical variables that most informatively differentiate the subjects.

Aim 2:

Aim 2 will utilize a prospective, single blind, randomized clinical trial design. Subjects from Aim 1 will comprise the study sample. Subjects will undergo testing twice.

We will use a repeated-measures ANOVA model with between-subjects factors that include interactions, to determine the effect of TNMT compared to HOME or STAN treatment on clinical performance after ACLR. Specifically, for a response of interest y , e.g., hip abductor strength, for the i^{th} subject in the k^{th} treatment group, with $l = 0$ indicating before intervention and $l = 1$ indicating after,

$$y_{ikl} = \alpha + \delta_l + (\gamma\delta)_{kl} + \tau_{i(k)} + \epsilon_{ikl}$$

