with (i) intercept α , (ii) subject random effect $\tau_{i(jk)} \sim N(0, \sigma_{\alpha}^2)$, (iii) pure error (or noise) $\epsilon_{ijk1} \sim N(0, \sigma_{\epsilon}^2)$, (iv) δ_l is the main effect due to intervention, and (vi) $(\gamma\delta)_{kl}$ is the interaction effect allowing intervention efficacy to vary with intervention type. The fixed effects are constrained such that $\delta_0 = (\gamma\delta)_{k0} = 0$. In this model, the baseline (i.e., pre-treatment) response for an individual is:

$$y_{ikl} = \alpha + \tau_{i(k)} + \epsilon_{ikl}.$$

Thus, the pre- intervention response for a given subject is the same regardless of which intervention group k they were assigned to, since nothing would have happened yet within their intervention group to distinguish them from other groups. Under the formulation in (1), the difference between observations before and after intervention is:

$$d_{ijk} = y_{ijk1} - y_{ijk0} = \delta^* + \gamma_k^* + \epsilon_{ijk}^*$$

where $\delta^* = \delta_1$, $\gamma_k^* = (\gamma\delta)_{k1}$, and $\epsilon_{ijk}^* = (\epsilon_{ijk1} - \epsilon_{ijk0}) \sim N(0, 2\sigma_{\epsilon}^2)$. The primary inference of interest is with respect to the relative efficacy of rehabilitation type γ_k^* and the effect of risk group on intervention efficacy, along with their interaction $(\beta\gamma)_{jk}^*$. Thus, this inference could equivalently be conducted using the pairwise differences in a straightforward one-way ANOVA model. We will assess model assumptions (e.g., normality and constant variance) via residual diagnostics and apply transformations if needed. Where appropriate, we will also utilize Tukey HSD post hoc analysis to further determine significance between groups on intervention effect.

Endpoints

There will be no known direct medical benefits to subjects from participating in this study.

Primary: Completion of all study activities

Secondary: Second injury

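### Aim 2: a one-way ANOVA on Post-minus-Pre differences is not equivalent to the printed common-baseline model; it is less precise, drops patients without a Post-Test, and can be biased by arm-dependent dropout

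*Combined protocol and SAP*

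**What the plan says.** The Aim 2 part of the Data Analysis Plan names the main analysis: "We will use a repeated-measures ANOVA model with between-subjects factors that include interactions". The printed model has an intercept, a time effect, an arm-by-time effect that is zero before intervention, and a normal random effect for each subject. It has no arm effect at baseline, and the plan explains why: "the pre- intervention response for a given subject is the same regardless of which intervention group k they were assigned to". The plan then forms each patient's Post-minus-Pre difference and concludes: "Thus, this inference could equivalently be conducted using the pairwise differences in a straightforward one-way ANOVA model".

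There are two measurements per patient: "Subjects will undergo testing twice". Substantial loss is expected. Subject Information, Target accrual, says: "Anticipating a 30% dropout rate, this will yield a final accrual of 120 subjects". The Power Statement says: "an accrual of 116 (with an estimated 30% dropout rate) subjects will be sufficient".

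The documents do not define an analysis set, a fitting method for the mixed model, a rule for a randomised patient with no Post-Test, or a missing-data sensitivity analysis. The only chasing of missing information, under Tracking, concerns unanswered surveys.

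**The concern.** The word 'equivalently' gives the analyst a free choice between two estimators that differ in precision, in the patients they use and in what they assume about dropout. With two visits, one missed Post-Test leaves no difference score, so the Pre-Test is lost as well. The comparison then becomes one among completers.

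Dropout could plausibly differ by arm. Under Differential Rehabilitation, TNMT patients "will participate in 12 sessions of supervised outpatient physical therapy over a six to eight week period", while STAN patients receive no training. At a correlation of 0.3, change depends strongly on the Pre value. Losing patients selectively on that value moves the mean change of those who remain, and moves it unequally if the selection differs by arm. The contrast of TNMT with HOME or STAN can then shift with no treatment effect present.

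**Working it through.** **Inputs from the documents.** Correlation 0.3 (Power Statement, which calls it likely conservative); two tests; three arms ("they will be randomized into one of three groups for differential treatment"); 30% dropout.

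The plan's dropout arithmetic does not reproduce: 150 × 0.70 = 105, not 120 (120/150 implies 20% loss), and 87/0.70 ≈ 125, not 116 (87/116 = 0.75 implies 25%). That is a separate matter, but it leaves the intended rate uncertain.

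**Assumptions.** 150 randomised, 50 per arm (no allocation ratio is stated); outcome SD 1 at both tests; higher is worse; no true arm effect; dropout logistic in the Pre value. The arm-specific rates and slopes are assumed, because the documents give none.

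**1. Why the two are not equivalent.** Write ρ for the correlation. The difference analysis contrasts mean Post minus 1 × mean Pre. The printed model, because the Pre mean is common to all arms, in effect contrasts mean Post minus ρ × mean Pre. Equivalence would hold, with complete data, for a model with a separate Pre mean in each arm. The printed model excludes that term.

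**2. Precision.** Variance per patient is 2(1 − ρ) = 1.40 for a difference and 1 − ρ² = 0.91 for the printed model.
- Complete data, 50 per arm: √(2 × 1.40/50) = 0.237 against √(2 × 0.91/50) = 0.191. Simulation gave 0.240 and 0.194.
- 30% without a Post-Test, 35 per arm: √(2 × 1.40/35) = 0.283 against √(2 × 0.91/35) = 0.228.

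**3. Dropout driven by the observed Pre value.** With no effect, the expected change given Pre is −(1 − ρ) × Pre, a slope of −0.7. With m the mean Pre value among completers, the bias of TNMT minus STAN on difference scores is −(1 − ρ)(m_TNMT − m_STAN).

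| Dropout STAN / TNMT | Log-odds slope per SD | m_STAN | m_TNMT | Bias, ρ = 0.3 | Bias, ρ = 0.7 |
|---|---|---|---|---|---|
| 20% / 40% | 0.5 | −0.096 | −0.189 | 0.065 | 0.028 |
| 20% / 40% | 1 | −0.173 | −0.332 | 0.111 | 0.048 |
| 10% / 20% | 1 | −0.091 | −0.173 | 0.058 | 0.025 |
| 30% / 30% | 1 in both arms | −0.253 | −0.253 | 0 | 0 |

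For row 2: −0.7 × (−0.332 + 0.173) = 0.111. A simulation of that case (40% in TNMT, 20% in the other arms, 3,000 trials) gave 0.113 for difference scores and 0.000 for the printed model fitted by maximum likelihood to all patients with a Pre-Test. The SDs of the contrast were 0.284 and 0.233. Dropout unrelated to Pre gives no bias even when the rates differ by arm.

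**4. Dropout driven by the stable subject effect.** Now Pre and Post shift together, so differences are unbiased. The printed model is biased by about (1 − ρ)√ρ × (difference in completer means of the standardised subject effect). At ρ = 0.3 and 20%/40% dropout this is 0.7 × 0.548 × (−0.093) = −0.04 SD for slope 0.5, and 0.7 × 0.548 × (−0.159) = −0.06 SD for slope 1 (simulated: −0.07). With 30% in both arms and slope 1 in TNMT only, it is 0.7 × 0.548 × (−0.253) = −0.10 SD.

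**The case against.** **The difference ANOVA is permitted, not prescribed.** This stands. The stated analysis is the repeated-measures model, and the sentence may be only a remark on the algebra. A reader might infer that the trial will report a completers comparison as its result; the documents do not say so. They also do not commit to a likelihood fit on all patients, and a repeated-measures ANOVA restricted to complete cases would drop the same patients.

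**The printed model is not safer in every case.** This also stands. It is tempting to say that it needs a weaker assumption about dropout. It does not: step 4 shows that neither assumption contains the other, and dropout driven by a patient's underlying function is plausible.

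**The size rests on chosen inputs.** This largely stands. Enrolment precedes surgery, while randomisation follows clearance for sport, so part of the 30% may leave before randomisation and cannot bias the randomised contrast. Patients who live too far away for weekly training are not allocated to TNMT, and all patients are contacted weekly during training; both features may limit differential loss. Missing training sessions is not the same as missing the Post-Test. In simulations with 20/30/40% dropout (STAN/HOME/TNMT), global type I error was only about 5% to 7%. It reached 18% only when selection ran in opposite directions in TNMT and STAN, for which the documents give no basis.

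None of this makes the equivalence true or supplies the missing analysis set.

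**Conclusion.** The equivalence claim is wrong and should be removed. The firm part is precision: even with complete data, the printed model has 0.91/1.40 = 65% of the variance of the difference analysis at correlation 0.3, and only it can keep patients who have a Pre-Test alone.

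The bias is conditional. It requires the difference route to be used and post-randomisation dropout to depend on the Pre value differently by arm. The central scenarios (20% against 40%) give about a quarter to two fifths of the contrast's standard error (0.07/0.28 to 0.11/0.28). The figure falls with higher correlation, lower dropout after randomisation or more similar selection across arms. The documents do not establish that the TNMT contrast will be biased, or in which direction.

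This is a worthwhile correction to the analysis plan, not a flaw in the design.

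**What to change.** In Aim 2, delete the equivalence sentence and state:

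> The Aim 2 analysis includes every randomised patient with a Pre-Test, in the arm assigned, whether or not Post-Testing was done. The model above (common Pre mean, arm-by-time effect, subject random effect) is fitted by REML to all available Pre and Post values, and arm contrasts are taken from it.

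Then add:
- the difference-score ANOVA, only as a sensitivity analysis labelled as completers only;
- one sensitivity analysis that shifts unobserved Post values by a pre-specified amount in each arm;
- a report of dropout after randomisation by arm and by Pre value.

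The cost is wording and two sensitivity runs, with no new data or patients. The downside is that the main analysis then relies on dropout depending only on arm and the observed Pre value. The two sensitivity analyses probe that assumption: the difference score holds when a stable patient trait drives dropout, and the shift analysis covers dropout related to the unseen Post value.

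### The listed endpoints do not serve the randomized question of Aim 2, and the four measures named in the power statement have no rank, no error control across them and only partly fixed definitions.

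*Combined protocol and SAP*

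**What the plan says.** **Endpoints** (end of the document) has two entries: "Primary: Completion of all study activities" and "Secondary: Second injury".

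**Data Analysis, Power Statement** derives 87 evaluable subjects from one effect size of 0.17 for knee biomechanics, alpha 0.05, 80% power and correlation 0.3. It then says the accrual suffices for four measures: for the uninvolved limb, "limb transverse plane hip net moment impulse, frontal plane knee joint ROM"; then "initial contact sagittal plane knee moment asymmetry, and deficits of involved limb postural stability". They correspond to the four predictors of second injury described in the Background.

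**Data Analysis Plan, Aim 2** writes the model for a generic response, with hip abductor strength as the example. It states: "The primary inference of interest is with respect to the relative efficacy of rehabilitation type", to which it adds "and the effect of risk group on intervention efficacy, along with their interaction". For multiplicity it says: "we will also utilize Tukey HSD post hoc analysis to further determine significance between groups".

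**Tracking** sets monthly injury surveys for two years after training, then yearly contact, six years in total.

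The form's own text under Data Analysis notes: "Power analyses and study endpoints are not required for minimal risk research, pilot or feasibility studies".

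**The concern.** Aim 2 is the randomized part of the study, and no outcome is designated to decide it. Completion has no hypothesis, no arm comparison and no power calculation. Second injury underlies Aim 1 and the Exploratory Aim and is followed for six years, but the analysis plan never compares it by arm. The measures that could answer Aim 2 are named only in the Power Statement.

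As the plan stands, the choice of measure that supports a claim for TNMT can be made after the results are known. So can the choice of task, limb or metric for that measure. A claim reached that way carries a higher false-positive risk than the nominal 0.05 suggests.

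**Working it through.** **1. Which outcome has what.**

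| Outcome | Listed endpoint | Named in Power Statement | Between-arm analysis specified |
|---|---|---|---|
| Completion | primary | no | no |
| Second injury | secondary | no | no |
| Hip moment impulse, knee ROM, knee moment asymmetry, postural stability | no | yes | only through a generic response |

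**2. Error across the four measures.** Assumption: each is tested at 0.05. The plan gives 0.05 only as the sample-size alpha.

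- Independent omnibus tests: 1 − 0.95^4 = 1 − 0.8145 = 18.5%.
- Correlated measures: null simulation, 20,000 runs, three arms of 35, equicorrelated normal change scores. The correlations are assumed, because the documents give none between measures.

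| Correlation between measures | Any false omnibus result | Any false Tukey pair favouring TNMT |
|---|---|---|
| 0 | 19.0% | 7.4% |
| 0.3 | 17.2% | 6.3% |
| 0.5 | 15.3% | 5.5% |
| 0.7 | 13.4% | 4.9% |

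For one measure, the rate of a false Tukey pair favouring TNMT is about 1.8%. As a check, 1 − (1 − 0.018)^4 = 7.0%. With arms of 29, of 40, or of 21 TNMT and 42/42, the ranges are 4.6-7.3% (TNMT) and 13.5-19.0% (omnibus).

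**3. Definitions within a measure.**

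- Fixed: the limb for hip impulse and for postural stability, initial contact at 10 N, and balance scores averaged over three trials.
- Open: the landing task (four are described), the limb for knee ROM, the impulse window and the asymmetry formula.
- Open for postural stability: three centre-of-pressure metrics and two eye conditions. Static versus dynamic is also open, unless the 30-second one-foot stance settles it.

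Chance of a false Tukey result favouring TNMT on one measure if every version is tried, at an assumed correlation between versions of 0.9 to 0.5:

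- Postural stability, 3 metrics × 2 eye conditions = 6 versions: about 4-8%.
- Postural stability, × 2 for static/dynamic = 12 versions: about 5-13%.
- Knee ROM, up to 4 tasks × 2 limbs = 8 versions: about 5-10%.

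No count is given for hip impulse or moment asymmetry, because an open window or formula has no natural maximum.

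**4. Power cost of controlling the error.** Inputs: 0.17 read as Cohen's f (the metric is not stated), two tests, correlation 0.3, three equal arms. Noncentral F with 2 and N − 3 df, λ = 0.17² × N × 2 / (1 − 0.3). The N values are 87 (Power Statement), 105 = 150 × 0.70, and 120 (Target accrual).

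| N | λ | Power at 0.05 | Power at 0.05/4 = 0.0125 |
|---|---|---|---|
| 87 | 7.18 | 65% | 43% |
| 105 | 8.67 | 74% | 54% |
| 120 | 9.91 | 80% | 62% |

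On this reading the plan's 80% at N = 87 is not reproduced. That is a separate question, and nothing in steps 1 to 3 depends on it.

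**The case against.** The strongest defence is the form's own statement that endpoints are not required for minimal risk research. On that view the list is an administrative entry and the Power Statement shows what matters. This limits how serious the point is. It does not remove it: the document describes Aim 2 as a randomized clinical trial and gives both a power statement and an endpoint list. If the four measures are taken as primary in effect, they still lack a success rule.

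Three narrower objections have some force.

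- *The plan does label something primary.* It does: the inference on rehabilitation type. A reader might infer that completion is the only result called primary, and that would be wrong. What is missing is the outcome to which the inference applies.
- *The task may be implied.* Only the drop vertical jump description says its trials will be processed as well as collected. That is suggestive, but no measure is tied to a task.
- *The four measures are not strictly what the trial was sized on.* One generic knee effect was used and then extended to them, and to all variables of interest. That is correct, and it leaves the ranking just as open.

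**Conclusion.** The point holds and should be corrected. The endpoint list does not serve Aim 2. The four measures named in the Power Statement are unranked and have no error control across them. Testing each at 0.05 gives about 18-19% (independent) to 13% (correlation 0.7) for any false omnibus result, and about 7% to 5% for a false Tukey result favouring TNMT. These sizes rest on the assumed per-measure alpha and correlations; the missing designation does not.

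Two stronger readings are not supported.

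- A reader might infer that second injury is neglected. It is followed for six years and underlies Aim 1 and the Exploratory Aim; only the comparison by arm is absent.
- A reader might count the risk-group effect and its interaction as two further primary tests per measure and arrive at a much larger error. The written Aim 2 equations contain no risk-group term, and the text says the inference reduces to a one-way ANOVA. That text and those equations need reconciling separately, and no error rate should be built on them.

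**What to change.** Replace the Endpoints section before arm-level outcome data are seen. If they have been seen, label the choice post hoc.

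- **Primary for Aim 2:** pre-to-post change in the four measures of the Power Statement, compared by arm with the omnibus test under the Aim 2 model, Holm-adjusted across the four at overall alpha 0.05. A claim for TNMT on a measure also needs a Tukey HSD pair favouring TNMT, at the level at which that measure's omnibus test was passed.
- **Alternative:** name one of the four as primary at 0.05. Test the other three by Holm only if the primary omnibus test and a Tukey pair favouring TNMT are both significant, with the same Tukey requirement for each secondary claim. Without the Tukey condition, a HOME-STAN difference could open the gate.
- **Definitions:** fix one version of each measure (task, limb, impulse window, asymmetry formula, centre-of-pressure metric, eye condition, static or dynamic).
- **Hypothesis 2B measures:** secondary with 95% confidence intervals and no confirmatory claim, or their own Holm family. The sponsor should decide this knowingly.
- **Risk-group effect and interaction:** exploratory, or kept primary with multiplicity control. This too is a knowing decision, because the current text includes them in the primary inference.
- **Second injury:** reported by arm at two and six years with 95% confidence intervals, descriptive.
- **Completion:** reported as retention.

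The Holm rule holds the null omnibus error across the four at about 4.8% (independent) and 3.8% (correlation 0.7). The cost is wording plus power: the first-step figures above apply to each measure. If all four effects are of the planned size and the arms are equally spaced in the hypothesised order, Holm's later steps raise the chance for any given measure to about 51-52%, 62-64% and 70-73% at N = 87, 105 and 120, before the Tukey requirement. Keeping 80% at 0.0125 would need 166 evaluable subjects, or 166/0.70, rounded up to 238 enrolled.
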